6.1.2 Supportive treatment/precautions

Because the LGX818 and MEK162 or LGX818 and MEK162 and LEE011 combination could trigger photosensitizing reactions, it is recommended that patients should be instructed to avoid exposure of skin and eye to direct sunlight as much as possible and to apply sun protection (e.g. sunscreen, sunglasses and protective clothing), for the duration of the trial and for at least 1 week after discontinuation of trial treatment. Any symptoms of photosensitivity must be reported on the Adverse Event eCRFs and institutional standard-of-care treatment should be initiated promptly.

For skin toxicity or nausea/vomiting prophylactic treatment may be initiated in all patients at the dose level where these toxicities have been observed and in all further patients if at least 1 patient has experienced skin toxicity or nausea/ vomiting \geq CTCAE Grade 3 or if at least 2 patients experienced skin toxicity or nausea/ vomiting \geq CTCAE Grade 2. However anti-emetics may be applied for treatment if the patient has experienced nausea/vomiting CTCAE Grade \geq 1, at the discretion of the physician.

For rash-like events, institutional standard-of-care treatment should be initiated promptly upon occurrence of such events. Treatment of rash may include, but is not limited to, topical or oral antibiotics, topical or oral anti-inflammatories, topical or oral corticosteroids and oral anti-histamines. The use of emollients and sunscreens has not been evaluated with LGX818/MEK162 or LGX818 /MEK162 /LEE011 but may be used prophylactically or as treatment for rash (see also [Appendix 3, Section 14.3.1](#) for guidelines for the treatment of study drug combination induced skin toxicity).

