Grade 3	Interrupt dosing of LGX818 and MEK162 (and maintain dose level of LEE011 in patients treated in triple-combination arm) and refer patient to ophthalmologist monitoring within one week. ^g - If resolved to Grade ≤ 1 in ≤ 21 days, reduce 1 dose level ^h of LGX818 and MEK162 - If not resolved to Grade ≤ 1 in > 21 days, discontinue patient from study drug treatment and refer the patient to an ophthalmologist for monitoring. ^h
Grade 4	Discontinue patient from study drug treatment and refer the patient to an ophthalmologist for monitoring. ^g
Skin and subcutaneous tissue disorders	
Rash / hand foot skin reaction (HFSR) / photosensitivity / Toxic Epidermal Necrolysis (TEN)	
Grade 1	Maintain dose level of LGX818 and MEK162 (and LEE011 in patients treated in triple-combination arm), but consider initiating appropriate skin toxicity therapy (See Appendix 3).
Grade 2	Maintain dose level of LGX818 and MEK162 (and LEE011 in patients treated in triple-combination arm), but initiate/intensify appropriate skin toxicity therapy.
Grade 3 despite skin toxicity therapy	Interrupt dosing of LGX818 and MEK162 (and LEE011 in patients treated in triple-combination arm), until resolved to Grade ≤ 1 then: - If resolved in ≤ 7 days, ↓ 1 dose level* of LGX818 and MEK162 (and LEE011 in triple-combination arm) - If not resolved after > 7 days, discontinue patient from study drug treatment.
Grade 4 despite skin toxicity therapy	Discontinue patient from study drug treatment.

Recommended Dose Modifications for (dual) LGX818 and MEK162 or (triple) LGX818 and MEK162 and LEE011 combination study treatment	
Worst Toxicity CTCAE v4.03 Grade (unless otherwise specified)^a	Recommended Dose Modifications any time during a cycle of therapy
Respiratory, thoracic and mediastinal disorders	
ILD/Pneumonitis	Maintain dose level of LGX818; adjust dose of MEK162 (and LEE011 in patients treated in triple-combination arm) according to Grade below
Grade 1	No dose interruption or adjustment of MEK162 (or LEE011 in patients treated in triple-combination arm) is required. Initiate appropriate medical therapy and monitor as clinically indicated

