6.4 Concomitant medications

6.4.1 Permitted concomitant therapy

The patient must be told to notify the investigational site about any new medications he/she takes after the start of the study drug combination. All medications (other than study drugs) and significant non-drug therapies (including herbal medicines, physical therapy and blood transfusions) administered during the study must be listed on the Concomitant medications/Significant non-drug therapies eCRF.

Patients taking concomitant medication chronically should be maintained on the same dose and dose schedule throughout the study period, as medically feasible. The days of full PK blood sampling should be representative of the other study days with regard to the use of the chronically administered concomitant medications. However, if a concomitant medication is used intermittently during the study, this medication should be avoided on the days of full PK sampling, if medically feasible.

The use of bisphosphonates regardless of indication is allowed for the LGX818 and MEK162 dual combination (prophylactic treatment is not allowed for bisphosphonates with LEE011) provided patients have been on stable doses for at least 2 weeks prior to study entry. Stable doses should be maintained during the treatment period. Patients requiring initiation of bisphosphonates during the course of the study should be discontinued due to progressive disease unless disease progression can be completely ruled out and this is clearly documented in the patients' source documentation.

Chronic dosing of corticosteroids such as dexamethasone and prednisone is known to lead to induction of CYP3A enzymes, thereby potentially increasing the risk of reducing drug exposure for CYP3A substrates to subtherapeutic levels. The following forms of corticosteroid treatment are permitted:

- Topical applications (e.g. rash), inhaled sprays (e.g. obstructive airway diseases), eye drops, or local injections (e.g., intra-articular);
- A short duration (< 5 days) of systemic corticosteroids \leq to the anti-inflammatory potency of 4 mg dexamethasone (e.g., for chronic obstructive pulmonary disease, or as an antiemetic).

Refer to the LGX818 Investigator's Brochure, MEK162 Investigator's Brochure and LEE011 Investigator's Brochure as applicable for information on possible interactions with other drugs.

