Patients receiving such medications above must be carefully monitored for potentiating of toxicity due to any individual concomitant medication, and may require dose titration of the drug substance. Investigators should use caution when prescribing co-medications, as clinical experience with these compounds in patients with cancer is often limited. Investigators should contact the Sponsor when they are unsure whether a drug should be prescribed to a patient in the clinical study. All concomitant medications and dietary supplements must be documented on the eCRFs. Please refer to [Appendix 4](#) for a list of medications to be used with caution as mentioned above.

6.4.2.1 Additional permitted concomitant therapy requiring caution and/or action for addition of LEE011 in the triple combination

LEE01 is a moderate substrate of P-glycoprotein (P-gp). LEE011 is a weak reversible inhibitor of CYP1A2. It is recommended that substrates metabolized predominantly by CYP1A2 with a narrow therapeutic index be taken with caution. LEE011 was found to inhibit the mitoxantrone-resistant protein (MXR or BCRP), and human bile salt export pump (BSEP). Medications to be used with caution during triple-combination treatment with LEE011 in this study are listed below (see [Appendix 4](#), as this list is not comprehensive and is only meant to be used as a guide. Please contact the medical monitor with any questions). These medications should be excluded from patient use if possible. If they must be given based on the investigator's judgment, then use with caution and consider a LEE011 interruption if the concomitant medication is only needed for a short time.

- Moderate inhibitors or inducers of CYP3A4/5 (may increase or decrease LEE011 exposure, respectively)
- Sensitive substrates of CYP3A4/5 that do not have narrow therapeutic index (LEE011 may increase exposure to these medications)
- Strong inhibitors of BSEP (based on *in vitro* data co-administration with LEE011 may lead to intrahepatic cholestasis)
- Medications that carry a possible risk for QT prolongation (may precipitate QT prolongation and TdP)
- Sensitive substrates of the renal transporters, MATE1, OCT2 and BCRP (has a potential to increase exposure to substrates of these transporters, although no animal or clinical data are available to support these statements)
- Strong inhibitors/inducers of P-gp.

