14.3.1 Rash

Skin disorder/rash has been observed in the ongoing studies of single-agent LGX818 and MEK162 and thus is recognized as a potential overlapping toxicity associated with the concurrent use of both compounds. The majority of these events were CTCAE Grade 1 or 2, but also dose-limiting as Grade 3 at the 80mg BID dose for MEK162.

The results of the STEPP study (Mitchell 2009; Piperdi 2009) support the use of pre-emptive skin treatment for patients at risk of treatment induced skin toxicity. In this study, the pre-emptive skin treatment regimen reduced the incidence of specific CTCAE Grade ≥ 2 skin toxicity by more than 50% as compared to the group who received only reactive skin toxicity treatment. In this study, patients will not initially receive prophylactic treatment for skin toxicity during Cycle 1. However, prophylactic treatment for skin toxicity may be introduced in subsequent cycles of treatment and in new patients if at least one patient has experienced CTCAE Grade 3 or greater skin toxicity, or if at least two patients have experienced such toxicities that are CTCAE Grade ≥ 2 . Prophylactic supportive therapy for skin toxicity (i.e. initiated 24 hrs prior to study drug combination) including skin moisturizers, sunscreen (PABA free, SPF ≥ 15 , UVA/UVB protection), topical steroid (1% hydrocortisone cream), and doxycycline (100 mg BID) may be initiated in all patients at the dose levels where these toxicities have been observed and may be advised to all further patients. Effective medications also include antihistamines, topical corticosteroids and low-dose systemic corticosteroids (the latter should be used with caution due to the increased risk of hyperglycemia).

The treatment algorithm is as follows:

Mild Rash (CTCAE Grade 1)

- Treatment with LGX818 and MEK162 or LGX818 and MEK162 and LEE011 should be maintained at the current dose.
- Topical hydrocortisone (1% or 2.5% cream) for macular rash and/or topical clindamycin (1%) for pustular rash is recommended.
- The patient should be reassessed after 2 weeks.

Moderate Rash (CTCAE Grade 2)

- Treatment with LGX818 and MEK162 or LGX818 and MEK162 and LEE011 should be maintained at the current dose, and the rash should be closely monitored for change in severity.

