- Doxycycline or minocycline are not recommended due to phototoxicity and should be replaced with oxytetracycline or lymecycline. However, if doxycycline or minocycline are used, precaution measurements should be taken (i.e., avoid direct exposure on sun, use of sunglasses, sunscreen, ect.). The recommendation is: topical clindamycin (1%) plus either

hydrocortisone (2.5% cream) or pimecrolimus (1% cream) plus oxytetracycline (500 mg twice daily) or lymecycline (408 mg QD).

Severe Rash (CTCAE Grade 3-4)

CTCAE Grade 3

- The dose of LGX818 and MEK162 or LGX818 and MEK162 and LEE011 should be omitted until resolved to CTCAE Grade ≤ 1 , in line with protocol recommendations, and the rash should be closely monitored for any change in severity.
- In addition to the interventions recommended for moderate rash, prednisolone may be given (with caution due to risk of hyperglycemia) as a reducing dose regimen (25 mg for 7 days, subsequently decreasing the dose by 5 mg/day every day to 0).
- If skin toxicity CTCAE Grade 3 is not resolved within 7 days, discontinue patient from study drug treatment.

CTCAE Grade 4

- If skin toxicity CTCAE Grade 4 occurs the dose of LGX818 and MEK162 or LGX818 and MEK162 and LEE011 should be omitted and patients discontinued from study drug treatment.

Table 14-7 Treatment of skin toxicity

Mild Rash (Grade 1) Dry Skin Nail changes Pruritus Desquamation Acneiform	Topical hydrocortisone 1% or 2.5% and/or Clindamycin 1% gel
Moderate Rash (Grade 2) Dry Skin Nail changes Pruritus Desquamation Acneiform	Topical clindamycin (1%) plus either hydrocortisone (2.5% cream) or pimecrolimus (1% cream) plus oxytetracycline (500 mg twice daily) or lymecycline (408 mg QD).
Severe Rash (Grade 3-4) Dry Skin Nail changes Pruritus Desquamation Acneiform	Hydrocortisone 2.5% cream or Clindamycin 1% gel or Pimecrolimus 1% cream plus oxytetracycline (500 mg twice daily) or lymecycline (408 mg QD) plus prednisolone (with caution due to risk of hyperglycemia) (25 mg for 7 days, decreasing the dose by 5 mg/day every day).
Adapted from Thatcher 2009 .	

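### Three concomitant-medication rules contradict each other: the length of a steroid course for Grade 3 rash, moderate CYP3A4 inducers in the triple, and two QT drugs in the triple; the impact is minor

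*Protocol*

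**What the plan says.** **Corticosteroids (dual and triple).** Section 6.4.1 explains that chronic dosing induces CYP3A and may lower exposure to CYP3A substrates, then lists what is permitted. Rash is named only under topical use. Systemic use is limited to "A short duration (< 5 days) of systemic corticosteroids", with a ceiling on potency. Appendix 3 (Section 14.3.1) says that for Grade 3 rash prednisolone may be given "as a reducing dose regimen (25 mg for 7 days, subsequently decreasing the dose by 5 mg/day every day to 0". Table 14-7 repeats this for severe rash: "plus prednisolone (with caution due to risk of hyperglycemia) (25 mg for 7 days". Both Appendix 3 and Table 6-4 hold study drug at Grade 3 until Grade 1 or better, and discontinue it if that takes more than 7 days.

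Two other texts mention systemic steroids without a duration. Section 6.1.2 includes "topical or oral corticosteroids and oral anti-histamines" among treatments for rash, and Appendix 3 adds: "Effective medications also include antihistamines, topical corticosteroids and low-dose systemic corticosteroids". Table 6-4 keeps dosing at Grades 1 and 2. At Grade 1 it tells sites to "consider initiating appropriate skin toxicity therapy (See Appendix 3"; at Grade 2 the dose is maintained, "but initiate/intensify appropriate skin toxicity therapy".

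**CYP3A4 inducers (triple).** Section 6.4.2.1 lists, for use with caution and exclusion where possible: "Moderate inhibitors or inducers of CYP3A4/5 (may increase or decrease LEE011 exposure, respectively". Section 6.4.3.1 prohibits strong inducers, and exclusion criterion 17 names only strong ones. Table 14-10 places strong and moderate inducers under one heading, footnoted as prohibited in the triple.

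**QT drugs (triple).** Section 6.4.3.1 prohibits drugs with a known risk; Section 6.4.2.1 puts possible-risk drugs under caution. Table 14-12 lists gatifloxacin and roxithromycin in both rows.

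**The concern.** LGX818 and LEE011 are both cleared mainly by CYP3A4, and LEE011 prolongs QTc. The co-medication rules are therefore part of how exposure and cardiac risk are controlled.

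A site that treats Grade 3 rash as Appendix 3 describes goes outside Section 6.4.1 as written. Section 6.1.2 sends sites to that appendix for skin toxicity. Section 12 allows no authorised deviations, and Section 10.3.3 reports the number and proportion of patients with deviations, so the same act could be recorded as compliant or as a deviation. In the triple, a site checking a moderate inducer, or one of the two antibiotics, finds a different answer depending on where it looks.

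**Working it through.** The plan gives no figure to reproduce. The check is a count of days and a comparison of texts.

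**1. Steroid course**

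Inputs: the regimen in Appendix 3, the limit in Section 6.4.1, and the hold rule in Table 6-4 and Appendix 3.

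- Days: 7 at 25 mg, then 20, 15, 10 and 5 mg on successive days. 7 + 4 = 11 dosing days.
- Dose: 7 × 25 + (20 + 15 + 10 + 5) = 175 + 50 = 225 mg.
- Limit: fewer than 5 days, so at most 4 whole days. The 7-day full-dose phase alone exceeds it.

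The two texts therefore conflict. The next question is how many of those days coincide with study drug. Assume that prednisolone starts when study drug is held, and that study drug restarts after r days of the course. A rash unresolved after 7 days means discontinuation, so r is at most 7. If the course is completed:

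- overlap = 11 − r days
- r = 7: 11 − 7 = 4 days, which is the taper (50 mg in total)
- r = 5: 11 − 5 = 6 days
- r = 3: 11 − 3 = 8 days

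The overlap stays within 4 days when the rash takes the full 7 days to resolve, and grows by a day for each day the rash clears sooner. Starting prednisolone later in the hold would lengthen it in the same way. Whether 25 mg of prednisolone meets the potency ceiling in Section 6.4.1 needs a conversion that the protocol does not give, so nothing here rests on it.

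**2. Moderate CYP3A4 inducers, triple**

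| Place | Strong | Moderate |
|---|---|---|
| Exclusion criterion 17 | excluded unless stopped 7 days before Cycle 1 Day 1 | not restricted |
| Section 6.4.2.1 | – | caution, exclude if possible |
| Section 6.4.3.1 | prohibited | not listed |
| Table 14-10 | prohibited | prohibited |

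Only the moderate column conflicts. The block in Table 14-10 has 15 entries and does not mark which are strong, so the number of moderate ones cannot be read from the document. Its heading also defines inducers by an AUC increase, whereas Section 6.4.2.1 says that inducers lower exposure. That is an error of direction, but it leaves no drug's status in doubt.

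**3. QT drugs, triple**

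Comparing the Known and Possible rows of Table 14-12 gives three shared names: gatifloxacin, roxithromycin and ondansetron. Ondansetron is separated by route (intravenous in one row, oral in the other), so two drugs carry two statuses. The table's footnotes make the classes exclusive: a clear association with torsades for Known, insufficient evidence of that risk for Possible.

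**The case against.** The strongest reply is that these are drafting slips with little consequence. Much of that stands.

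- *Steroids.* A reader might infer that the 7 of 11 days (125 of 225 mg) past the limit are all spent on study drug. The documents do not support that: at Grade 3 all study drug is held, and a rash unresolved after 7 days ends treatment. The course is also optional. What remains is that Section 6.4.1 makes no exception for held days, and overlap exceeds 4 days when the rash clears early and the course is finished. The reference to chronic dosing is the reason given for the rule; the rule itself is a list of permitted forms with a numeric limit.
- *Section 6.1.2 and low-dose systemic steroids.* A reader might count these as further contradictions, particularly with dosing kept at Grade 2. They are silent on duration, so the Section 6.4.1 limit can apply to them. The Appendix 3 algorithm gives no systemic steroid at Grade 1 or 2. They need a cross-reference, no more.
- *Inducers.* A reader might say that 15 drugs have an unclear status. Strong inducers are prohibited either way, and at least two entries are settled elsewhere: St. John's wort is named in Section 6.4.3.1, and ritonavir is prohibited as a strong inhibitor in the same table.
- *QT.* It is fair to say that a drug in the Known row is prohibited whatever another row says. The duplicate is clerical, but it still puts two prohibited drugs in the caution list.

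Sites that are unsure are told to contact the Sponsor or, for the triple, the medical monitor. This lowers the risk without making the texts agree.

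**Conclusion.** All three contradictions are present in the current text and should be corrected. Their impact is minor, and no endpoint, sample size or error rate is touched.

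The steroid conflict is one of duration: 11 days offered against at most 4 whole days allowed. On-drug overlap is about 4 days if dosing restarts after day 7, and longer only if the rash clears earlier and the course is completed. This assumes that prednisolone starts with the hold. The inducer conflict covers moderate inducers only, in unknown number. The QT conflict covers two drugs.

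At Amendment 10, 10 patients were on treatment (5 dual, 5 triple). These are ceilings on who is subject to the rules: 10 for steroids, 5 for the other two. They are not counts of patients with Grade 3 rash or taking the drugs concerned, and enrollment is closed.

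**What to change.** 1. **Steroids.** Add to Section 6.4.1 an exception for Grade 3 rash while study drug is held, with at most 4 days of systemic steroid after restart. Alternatively, shorten the course in Appendix 3 and Table 14-7 to the Section 6.4.1 limit. Cross-refer Section 6.1.2 and Appendix 3 to that rule.
2. **Inducers.** Give moderate CYP3A4 inducers one status in Sections 6.4.2.1 and 6.4.3.1 and Table 14-10, and confirm that exclusion criterion 17 agrees with it. Either status is workable and the choice is the Sponsor's. If caution is chosen, the list in Table 14-10 must be split into strong and moderate. Correct its heading to an AUC decrease.
3. **QT drugs.** Keep gatifloxacin and roxithromycin in the Known row only.

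A general clause that the stricter text prevails wherever Section 6 and the appendices differ is not advised. It would reach unrelated content, such as the liver thresholds in Appendix 8 and Table 6-4, without anyone having examined the effect.

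The cost is corrected text and tables. A letter can alert investigators at once, with the wording changed in the next amendment, as Section 12.1 requires. No new data or procedures are needed.

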6.4.2 Permitted concomitant therapy requiring caution and/or action for LGX818 and MEK162

LGX818 is a reversible inhibitor of CYP1A2, CYP2B6, CYP2C8/9, CYP2D6, CYP3A4, and UGT1A1. It is also a time dependent inhibitor of CYP3A4. Permitted medications to be used with caution in this study include those that are sensitive substrates of CYP1A2, CYP2B6, CYP2C8/9, CYP2D6, CYP3A4, and UGT1A1, or those substrates that have a narrow therapeutic index (NTI).

There is a potential for LGX818 to induce CYP3A4 at concentrations >10-50 uM, which may reduce the effectiveness of hormonal contraception methods. Therefore, the use of at least one form of non-hormonal contraception will be needed during the participation in this study. Please see [Section 5.3](#) exclusion criterion 10 for use of contraception methods required for this study.

LGX818 has been identified to be primarily metabolized by CYP3A4 *in vitro*. It is advised that LGX818 should be taken with caution when co-administered with moderate inhibitors of CYP3A4 or strong inducers of CYP3A4 (NB. strong systemic inhibitors of CYP3A4 are prohibited (please see [Section 6.4.3](#))).

In vitro data showed that both LGX818 and MEK162 are substrates of P-gp. Thus, the use of drugs that are known to inhibit or induce P-gp should be used with caution. LGX818 is a BCRP

and P-gp inhibitor. It is also a potent inhibitor of the renal transporters OAT1, OAT3 and OCT2 and the hepatic transporters OATP1B1 and OATP1B3. Therefore the co-administration of drugs that are known to be sensitive or NTI substrate of BCRP, P-gp, OAT1, OAT3, OCT2, OATP1B1, and OATP1B3 should be used with caution.

MEK162 is a substrate for many CYP isoforms, in particular CYP1A2 and CYP2C19. The risk of metabolic interaction caused by an effect on an individual isoform is therefore minimized. Nevertheless, caution should be used in patients receiving concomitant treatment with other drugs that are either potent inhibitors or inducers of these enzymes.

Patients receiving such medications above must be carefully monitored for potentiating of toxicity due to any individual concomitant medication, and may require dose titration of the drug substance. Investigators should use caution when prescribing co-medications, as clinical experience with these compounds in patients with cancer is often limited. Investigators should contact the Sponsor when they are unsure whether a drug should be prescribed to a patient in the clinical study. All concomitant medications and dietary supplements must be documented on the eCRFs. Please refer to [Appendix 4](#) for a list of medications to be used with caution as mentioned above.

6.4.2.1 Additional permitted concomitant therapy requiring caution and/or action for addition of LEE011 in the triple combination

LEE01 is a moderate substrate of P-glycoprotein (P-gp). LEE011 is a weak reversible inhibitor of CYP1A2. It is recommended that substrates metabolized predominantly by CYP1A2 with a narrow therapeutic index be taken with caution. LEE011 was found to inhibit the mitoxantrone-resistant protein (MXR or BCRP), and human bile salt export pump (BSEP). Medications to be used with caution during triple-combination treatment with LEE011 in this study are listed below (see [Appendix 4](#), as this list is not comprehensive and is only meant to be used as a guide. Please contact the medical monitor with any questions). These medications should be excluded from patient use if possible. If they must be given based on the investigator's judgment, then use with caution and consider a LEE011 interruption if the concomitant medication is only needed for a short time.

- Moderate inhibitors or inducers of CYP3A4/5 (may increase or decrease LEE011 exposure, respectively)
- Sensitive substrates of CYP3A4/5 that do not have narrow therapeutic index (LEE011 may increase exposure to these medications)
- Strong inhibitors of BSEP (based on *in vitro* data co-administration with LEE011 may lead to intrahepatic cholestasis)
- Medications that carry a possible risk for QT prolongation (may precipitate QT prolongation and TdP)
- Sensitive substrates of the renal transporters, MATE1, OCT2 and BCRP (has a potential to increase exposure to substrates of these transporters, although no animal or clinical data are available to support these statements)
- Strong inhibitors/inducers of P-gp.

